### 4.2.2. ANALYSIS METHODS

The primary efficacy endpoint of 6 month response proportion will be assessed using a 2sided exact test to determine whether the proportion of responders is significantly different than 0.5. Only subjects in the 6ME set will be included in the primary endpoint analysis. The corresponding exact (Clopper-Pearson) 2-sided 95% confidence interval will be calculated. The null hypothesis that the proportion of responders is = 0.5 will be rejected if the p-value is < 0.05.

#### SUPPORTIVE AND SENSITIVITY ANALYSES 4.2.2.1.

The primary endpoint analysis will be repeated using the PP analysis set. In order to quantify the impact of missing data on the primary analysis results, missing data may be imputed using 2 techniques:

- Last observation carried forward (LOCF) 1.
- Subjects with missing data classified as non-responders 2.

Since the efficacy of the device may deteriorate over time, LOCF represents the least conservative imputation technique, while classifying subjects with missing data as nonresponders represents the most conservative technique. These two analyses are reasonable upper and lower bounds for the response result, accounting for the missing data.

#### SUBGROUP ANALYSES FOR THE PRIMARY ENDPOINT 4.3.

Analyses of the primary efficacy endpoint in the 6ME analysis set will be performed to examine the consistency of implant effect across subgroups listed below (if there are no fewer than 5-10 subjects within each subgroup level). The proportion of responders in each group and corresponding exact 95% confidence interval for response rate will be presented.

- Investigator subgroups
- Type of procedure (SPX alone versus combinations with septoplasty and/or turbinate reductions)
- Turbinate reduction method: Radiofrequency versus Mechanical

#### MAJOR SECONDARY ENDPOINTS 4.4.

#### 4.4.1. DEFINITIONS

The secondary efficacy endpoints are:

- Proportion of treatment responders at 1, 3, 12, 18 and 24 months post procedure.
- Change in nasal airway obstruction from baseline to 1,3, 6, 12, 18 and 24 months as reported by subjects on the VAS scale.
- Subject satisfaction questionnaire at 6 months.
- Procedure and device-related adverse events though 24 months.

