To date, all follow up visits through 18 months have been completed; 15 out of 30 subjects completed 18 months of follow up. Three subjects have had other nasal surgery procedures and consequently exited the study; two subjects after the 12 month visit and one subject after the 18 month visit.

		Score	Change from baseline			Change from baseline % Change from baseline			Change from baseline	
Visit	N	Mean (SD)	Mean (SD)	LS Mean (95% CI)	p-value	Mean (SD)	LS Mean (95% Cl)	p- value		
1 Week	30	24.2 (16.14)	-52.5 (22.77)	-52.7 (-58.83, -46.55)	<.001	-67.2 (21.34)	-67.2 (-74.98, -59.51)	<.001		
1 Month	30	27.0 (23.95)	-49.7 (25.56)	-49.9 (-58.79, -40.93)	<.001	-64.8 (29.09)	-64.9 (-75.92, -53.86)	<.001		
3 Months	29	28.4 (26.90)	-48.4 (27.84)	-47.9 (-57.85, -37.96)	<.001	-63.4 (34.45)	-62.7 (-75.70, -49.66)	<.001		
6 Months	30	33.3 (29.69)	-43.3 (31.28)	-43.5 (-54.61, -32.44)	<.001	-56.2 (37.85)	-56.3 (-70.46, -42.07)	<.001		
12 Months	29	35.2 (29.17)	-40.9 (31.23)	-39.7 (-51.22, -28.11)	<.001	-53.1 (40.64)	-51.6 (-67.07, -36.12)	<.001		
18 Months	15	38.0 (33.32)	-41.7 (36.24)	-40.7 (-55.01, -26.30)	<.001	-51.3 (41.76)	-52.2 (-70.59, -33.87)	<.001		

A longitudinal summary of NOSE score is provided in the table below and these results demonstrate significant improvements over baseline for all time points measured.

This first in man study demonstrated the safety and effectiveness of the absorbable Implant to provide lateral cartilage support in patients with NVC as primary contributor to NAO.

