7.7. STUDY SCHEDULE OF EVENTS TABLE

Study Events	Screening & Enrollment (Visit 1)	Baseline Evaluation (Visit 2) ¹	Treatment (Visit 3)	Follow Up 1 mo (Visit 4)	Follow Up 3 mo (Visit 5)	Follow Up 6 mo (Visit 6)	Follow Up 12 moStudy Visit (Visit 7)	Follow Up 18 & 24 mo/Final Study Visit (Visits 8 & 9)	Early Exit
Secure Informed Consent	Х								
Secure Re-Consent for 18M and 24M Follow Up							Х		
Inclusion/Exclusion	Х		X ²						
NOSE Scale (PRO) ³	Х	Х	X ²	Х	Х	Х	Х	Х	
NAO Breathing Assessment (PRO)		Х		Х	Х	Х	Х	Х	
Subject Satisfaction Questionnaire (PRO)				Х	Х	Х	Х		
Health Economics Questionnaire (PRO)		Х		Х	Х	Х	Х		
Nasal Medical History/Nasal Geometry		Х							
Nasal Exam		Х		Х	Х	Х	Х		
Lateral Wall Motion Video		Х				Х			
Photography- 3D Camera (select sites)		Х			Х	Х	Х		
Photography –Cosmetic (select sites)		Х			Х	Х			
Turbinate Hypertrophy Contribution to		Х							
NAO assessment (Nasal Decongestant)									
Photography – Planning Images			Х						
NAO Treatment			Х						
Concomitant Medications		Х	Х	Х	Х	Х	Х		
Adverse Event Assessment			X	X	X	X	Х		Х
Adverse Device Effects Assessment								X	
Complete Study Exit Form								X ⁴	Х

¹ Visit 2 activities may be done in conjunction with Study Visit 1. In this instance, the Screening NOSE Scale is not required.

² If Visit 3 (Treatment Visit) is more than 1 month after Visit 1, inclusion/exclusion criteria need to be re-confirmed. Additionally, subjects should be asked to review IC form, initial and date the IC document to confirm continued consent for participation, and complete NOSE scale.

³ If Visits 1, 2 and 3 are done on the same day, the Screening and Treatment NOSE Scales are not required.

⁴To be completed at 24M follow up.

Spirox Latera™ implant support of lateral wall cartilage (LATERAL-OR) study	
SPI-CP-301	Sep

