10.4.3. ANALYSIS OF THE SECONDARY ENDPOINT(S)

Response proportion as defined in section 10.4.2 will be evaluated for the 1, 3,6, 12, 18 and 24 month follow-up visits using the same technique as described for the primary endpoint.

Spirox Latera™ implant support of lateral wall cartilage (LATERAL-OR) study	Version 2.0
SPI-CP-301	September 7, 2017

Change in nasal airway obstruction from baseline at 1,3, 6, 12, 18 and 24 months post-procedure as reported by subjects on a VAS 0-100 mm scale (0= no difficulty breathing through nose; 100mm=not-able to breathe through nose) will be analyzed using a mixed model for repeated measures (MMRM). Least-square mean change from baseline and corresponding 95% confidence intervals will be reported. Baseline VAS score will be analyzed in a separate model, including decongestant use as a covariate. Decongestant use will be considered at baseline only to visualize the turbinate contribution to overall obstruction, thus no decongestant VAS will be assessed at the follow-up visits.

Results from the subject satisfaction questionnaire will be tabulated at 6 months. Sensitivity analyses for missing data will be described in the SAP.

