# 2.2.1. ANALYSIS SETS FOR EFFICACY AND SAFETY

The ITT analysis set will primarily be used for safety evaluations and will include all subjects who begin the implant procedure. Subjects who are consented but do not begin the implant procedure will not be included in the ITT analysis set. Because this is a singlearm, open-label study, the exclusion of subjects who do not begin the implant procedure is unlikely to result in biased response estimates. Subjects who begin the implant procedure but do not successfully receive an implant will be included in the ITT analysis set.

The mITT analysis set will consist of all subjects who successfully receive at least 1 Spirox LateraTM implant. Analyses supporting the primary and major secondary endpoints will, to the extent possible, be based on the mITT analysis set. Safety evaluations for events within 7 days of the implant procedure will be based on the ITT analysis set, and cumulative adverse events at 6 months will be based on the mITT analysis set. An important subgroup of the mITT analysis set is the 6 Month Evaluable (6ME) Set, which includes subjects with 6 month post-implant NOSE score assessments in clinic or by telephone.

The per-protocol (PP) analysis set will consist of all mITT subjects who have no major protocol deviations or events that might impact NOSE scores. These deviations may include changes to background nasal medications, prohibited medications and additional procedures prohibited by the protocol.

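### The 18- and 24-month responder rates may be overstated: the protocol makes them observed-case, and the SAP gives them no method and no missing-data analysis

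*SAP*

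**What the plan says.** **Endpoint.** SAP 4.4.1 lists "Proportion of treatment responders at 1, 3, 12, 18 and 24 months post procedure" among the major secondary endpoints.

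**Method.** Protocol 10.4.3 evaluates the response proportion at these visits "using the same technique as described for the primary endpoint". That technique is a two-sided exact test with a Clopper-Pearson interval in the 6-month evaluable subjects (Protocol 10.4.2). SAP 4.2.2 is explicit: "Only subjects in the 6ME set will be included in the primary endpoint analysis". SAP 4.4.2, the methods section for the secondary endpoints, covers the VAS, baseline decongestant use and the satisfaction questionnaire. It does not mention the later responder proportions. SAP 2.2.1 adds a general statement: "Analyses supporting the primary and major secondary endpoints will, to the extent possible, be based on the mITT analysis set". It gives no rule for a treated subject who has no score at a visit.

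**Missing data.** Protocol 10.4.3 ends with "Sensitivity analyses for missing data will be described in the SAP". SAP 4.2.2.1 offers last observation carried forward (LOCF) and missing as non-responder, both optional and both tied to the primary analysis. Protocol 10.4.5 compares subjects with and without data at 6 months only.

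**Late follow-up.** Inclusion criterion 7 asks for agreement to 12 months of follow-up. The schedule in Protocol 7.7 has a row "Secure Re-Consent for 18M and 24M Follow Up", marked at the 12-month visit. The Early Exit column of that schedule marks adverse events and the exit form, but not the NOSE scale.

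**Prior study.** Protocol 2.2 reports that "15 out of 30 subjects completed 18 months of follow up". It also reports that three subjects had other nasal surgery and left the study, two after the 12-month visit and one after the 18-month visit.

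**The concern.** The implant absorbs over approximately 18 months (Protocol 6.2), and SAP 4.2.2.1 justifies its choice of imputations with "Since the efficacy of the device may deteriorate over time". The 18- and 24-month responder rates are therefore the trial's evidence on durability. As written, they will describe only the subjects who re-consented, stayed and returned a score.

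Three features of the plan could link staying to outcome. A subject who goes on to other nasal surgery may exit, as happened in the prior study. Willingness to re-consent at 12 months may depend on how the subject is doing. A subject who leaves early is not scheduled to give a final NOSE score. If poor outcomes leave more often, a completer rate can stay flat while the treated group worsens.

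The SAP repeats the efficacy analyses in the per-protocol set, but this does not help. Its definition (SAP 2.2.1) allows removal of subjects who had prohibited procedures.

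**Working it through.** **1. What estimate the text produces.** Carrying the primary technique to visit t gives p_obs(t) = responders at t / subjects with a NOSE score at t. No section of the SAP adds a second estimate for 12, 18 or 24 months.

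**2. The plan's own figures.** No response rate or power is stated for the later visits. The nearest figures are these:
- 24-month retention target (Protocol 5.3): 150 of 170 = 88.2%.
- 6-month power statement, 66% against 50%, two-sided 5% exact test: 93.0% power with the SAP's 120 subjects and 97.5% with the protocol's 150. Both agree with the stated power above 90%, but neither concerns late follow-up.

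**3. Counting missing as non-response.** Assumptions: all 170 enrolled are treated and in the mITT set, and 80% of observed subjects respond. The 80% is the prior study's 6-month rate, carried to later visits by assumption. With x responders among n observed, the observed-case rate is x/n, the lower bound is x/170, and the upper bound, with every missing subject a responder, is (x + 170 − n)/170. Intervals are exact 95%.

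| Retained | Observed-case | Missing as non-response | Missing as response |
|---|---|---|---|
| 150 (88.2%) | 120/150 = 80.0% (72.7 to 86.1) | 120/170 = 70.6% (63.1 to 77.3) | 140/170 = 82.4% |
| 136 (80%) | 109/136 = 80.1% (72.4 to 86.5) | 109/170 = 64.1% (56.4 to 71.3) | 143/170 = 84.1% |

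At the design rate of 66% the same steps give 99/150 = 66.0% against 99/170 = 58.2% (50.4 to 65.7), and 90/136 = 66.2% against 90/170 = 52.9% (45.1 to 60.6).

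For 12 months, Protocol 2.2 shows 29 of 30 subjects observed in the prior study. At that retention the lower bound is 0.80 × 29/30 = 77.3%.

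**4. What selective loss would do.** Let p be the true rate and k the retention of non-responders divided by that of responders. Then p_obs = p / (p + (1 − p)k). With p = 0.80:
- k = 0.9: 0.80/0.98 = 81.6%
- k = 0.75: 0.80/0.95 = 84.2%
- k = 0.5: 0.80/0.90 = 88.9%
- k = 1.25: 0.80/1.05 = 76.2%

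The values of k are assumptions. Below 1 the observed rate is too high; above 1 it is too low.

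**5. What the documents say about k.** Of the three surgery exits in the prior study, at most two can account for absence at 18 months, because the third came after that visit. That leaves 15 − 2 = 13 of the 15 subjects without 18-month data unexplained. Appendix II speaks of 18 subjects having reached 18 months, so not all 30 may have been due. The observed and model-based NOSE changes in Protocol 2.2 are close and do not all differ in one direction: −40.9 and −39.7 at 12 months, −41.7 and −40.7 at 18 months, but −51.3% and −52.2% for percentage change at 18 months.

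**The case against.** A reader might infer that durability will be overstated, or that the documents show informative loss. They do not go that far. Two surgery exits before the 18-month visit are a reason for care, not proof of a direction, and step 4 shows that the bias reverses if responders leave more often. Nor is the prior study's 15 of 30 a fair forecast of retention here: most of that shortfall has no stated cause, and this protocol plans for 150 of 170.

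Other points for the plan:
- Re-consent is taken at the 12-month visit, so it cannot affect the 12-month rate. This stands, and it makes the 12-month concern smaller.
- Data at 18 and 24 months may come by visit, telephone or mail, with a $100 payment each time (Protocol 5.3). This should reduce loss but does not say how the remaining loss is handled.
- SAP 4.4.1 states no denominator, and SAP 2.2.1 names the mITT set as far as possible. That is true. Observed-case follows from Protocol 10.4.3 read with 10.4.2 and SAP 4.2.2, and the mITT statement has no effect without a rule for absent scores.
- Protocol 10.4.2 lists the two imputations, so a reader could carry them to later visits together with the technique. The sensitivity-analysis sentence in 10.4.3 also follows directly on the questionnaire sentence and may refer only to that. Both readings are possible, but the SAP confines the imputations to the primary result.
- Secondary results are supportive and their p-values descriptive (Protocol 10.4.9, SAP 4.1.1). Disposition and follow-up time will be reported (SAP 3.3, 3.5), so attrition will be visible. The risk is therefore to the durability estimate, not to type I error.

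**Conclusion.** The point holds in a limited form. The later responder proportions are observed-case under the protocol, and the SAP supplies neither a method nor a missing-data analysis for them. With exits after surgery in the prior study, re-consent at 12 months and no NOSE score scheduled at exit, the 18- and 24-month rates may be overstated.

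For scale, an observed 80% has a floor of 70.6% at the protocol's own retention target and about 64% at 80% retention. These floors assume that every missing subject failed, which SAP 4.2.2.1 itself calls the most conservative choice. They show how far the completer rate leaves the answer open and do not measure bias. They rest on 170 treated and on an 80% late response rate that the documents do not give.

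**What to change.** In SAP 4.4.2, for 12, 18 and 24 months, report:
- (a) the observed-case proportion with its denominator and exact interval;
- (b) the mITT proportion with missing data and exit for other nasal surgery counted as non-response. Treating surgery exit this way is an estimand choice and should be stated as one.

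Optionally add one less extreme estimate, by multiple imputation or a repeated-measures logistic model. The SAP should not claim that it lies between (a) and (b): if earlier responders drop out more, it can exceed (a).

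Tabulate 12-month response for subjects who did and did not re-consent. This is the most direct evidence the trial can give on the direction of any bias.

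The cost is SAP wording, extra table rows and less favourable figures. No new data are needed.

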### 4.4.2. ANALYSIS METHODS

Primary endpoint will be analyzed using a mixed model for repeated measures (MMRM). The analysis will be based on observed data and will include the fixed, categorical effect of visit, as well as the continuous, fixed covariates of baseline VAS score and baselineby-visit interaction (if significant). An unstructured covariance matrix will be used to model the within-subject errors. If this model does not converge, a compound symmetry covariance matrix will be used. Least-square mean change from baseline and corresponding 95% confidence intervals will be reported.

A t-test will be used to determine if baseline VAS scores differ by Afrin use. Afrin use, to visualize the turbinate contribution to overall obstruction, will be used considered at baseline only.

Results from the subject satisfaction questionnaire, including a cosmesis assessment, will be tabulated at 6 and 12 months. These items will be summarized individually:

- Change in Nose Appearance: Worse, No Change, Better (collapsed from 5 categories)
- Subject Would Recommend Procedure
- Subject Would Repeat Procedure

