10.4. DESCRIPTION OF STATISTICAL METHODS

10.4.1. GENERAL APPROACH

This is a prospective, single arm, open label controlled study to evaluate the impact of Spirox Latera[™] alone or in conjunction with other procedures over 24 months of follow-up. Each patient will serve as his or her own control.

The study reference day (Day 1) is the day of the Implant procedure.

"Baseline" NOSE score refers to the measurement taken prior to the start of the procedure during the baseline visit.

Continuous variables will be summarized with descriptive statistics (N, mean, SD, median, quartiles), and categorical variables will be summarized as N (%).

Unless otherwise indicated, all p-values and confidence intervals will be 2-sided.

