#### INTRODUCTION 1.

This statistical analysis plan (SAP) contains the definitions of analysis sets, derived variables, and statistical methods for the analyses of efficacy and safety data from the Spirox LateraTM implant support of lateral nasal wall cartilage (LATERAL-OR) study, which is a multi-center, non-randomized, single arm study (Clinical Protocol SPI-CP-301). This study was designed to quantify changes in the symptoms of nasal airway obstruction associated with the use of the Spirox LateraTM implant. Subjects will be consented and enrolled prior to device implant, and assessed through 24 months post implant.

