#### ANALYSIS SPECIFICATIONS 4.1.

### 4.1.1. LEVEL OF SIGNIFICANCE

Unless otherwise specified, all statistical tests will be interpreted at a 2-sided significance level of 5% and all confidence intervals at a 2-sided confidence level of 95%. The study type 1 error rate of 5% will all be allocated to the primary endpoint hypothesis, so p-values beyond the primary hypothesis should be considered descriptive.

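### The single-arm VAS model treats the baseline mean as known, so its 95% intervals for mean change are somewhat too narrow for the population sampled

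*SAP*

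**What the plan says.** The endpoint in SAP 4.4.1 is "Change in nasal airway obstruction from baseline to 1,3, 6, 12, 18 and 24 months" on the VAS. SAP 4.4.2 fits a mixed model for repeated measures to observed data. Its terms are categorical visit, "continuous, fixed covariates of baseline VAS score", and a baseline-by-visit interaction that is kept only if significant. On covariance it states: "An unstructured covariance matrix will be used to model the within-subject errors". The opening sentence of 4.4.2 calls the outcome the primary endpoint, but the VAS covariate and Protocol 10.4.3 show that this is the VAS model.

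On reporting, Protocol 10.4.3 states: "Least-square mean change from baseline and corresponding 95% confidence intervals will be reported". SAP 4.4.2 says the same.

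On design, SAP section 1 describes a "multi-center, non-randomized, single arm study", and Protocol 10.4.1 states: "Each patient will serve as his or her own control". SAP 4.1.1 sets the confidence level at 95% and makes p-values beyond the primary hypothesis descriptive. Neither document puts baseline in the response vector, adds a variance term for the baseline mean, or limits inference to the baseline mean observed.

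**The concern.** An LS mean change is evaluated at the sample mean baseline, and its model-based standard error treats that mean as a fixed number. In a randomized comparison this matters little, because the baseline term largely cancels between arms. Here nothing cancels: the reported effect is follow-up mean minus baseline mean, and the baseline mean is an estimate from the same subjects. The narrowing occurs even when the unstructured model converges, so it is separate from the compound-symmetry fallback and from the interaction rule.

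At stake is the stated precision of VAS change at six visits. A descriptive endpoint is read through its estimate and interval, so an interval labelled 95% should cover at about that rate for the quantity a reader takes it to describe.

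**Working it through.** **Plan's own figure.** There is none to reproduce: the documents give no SD, correlation or precision for VAS. The sample-size figures (120 evaluable in the SAP, 150 in Protocol 10.5) concern the responder proportion. I use n = 150 below; the coverage results hardly depend on n.

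**Algebra.** Let X be baseline, Y follow-up, rho their correlation, k = SD(Y)/SD(X), and beta = rho·k.

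- Variance behind the planned interval: Var(Y|X)/n, with Var(Y|X) = Var(Y)(1 − rho²).
- Variance of the mean change over sampled subjects: [Var(Y|X) + (beta − 1)² Var(X)]/n.
- SE ratio, planned over correct: sqrt{k²(1 − rho²)/(1 + k² − 2·rho·k)}.
- Approximate coverage: 2Φ(1.96 × ratio) − 1.

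The omitted term is zero only when beta = 1.

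**Worked case (assumed).** Both SDs 20 mm, rho 0.5, n = 150. Planned: 400 × 0.75 = 300. Omitted: (0.5 − 1)² × 400 = 100. Ratio = sqrt(300/400) = 0.866, coverage 91.0%. The half-width is 2.79 mm as planned and 3.22 mm as a paired interval.

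**Range (assumed k and rho), coverage of the planned interval:**

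| k | rho 0.1 | rho 0.3 | rho 0.5 | rho 0.7 |
|---|---|---|---|---|
| 1.0 | 85.4% | 88.6% | 91.0% | 92.9% |
| 1.5 | 91.1% | 93.3% | 94.6% | 95.0% |
| 1.67 (SDs 15, 25) | 92.0% | 93.8% | 94.8% | 94.8% |
| 2.0 | 93.1% | 94.5% | 95.0% | 94.1% |

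Simulation agrees. One-visit trials with equal SDs (20,000 per setting) gave 85.6%, 88.5%, 91.3% and 93.0%, while the paired interval held 94.7% to 95.2%. A six-visit model with unstructured covariance and a common slope (600 trials per setting) gave 86.0%, 89.8%, 92.0% and 92.9%.

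**Prior-study table (Protocol 2.2, NOSE).** The raw half-width is t(n−1) × SD of change/√n. The LS half-width is half the printed interval. At 6 months: 2.045 × 31.28/√30 = 11.68, and (54.61 − 32.44)/2 = 11.09.

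| Visit | n | Raw | LS | Ratio | Implied coverage |
|---|---|---|---|---|---|
| 1 month | 30 | 9.54 | 8.93 | 0.94 | 93.3% |
| 3 months | 29 | 10.59 | 9.95 | 0.94 | 93.4% |
| 6 months | 30 | 11.68 | 11.09 | 0.95 | 93.7% |
| 12 months | 29 | 11.88 | 11.55 | 0.97 | 94.3% |

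At 1 and 6 months the LS half-width equals, within about 0.01, the one obtained from the follow-up score SD alone (2.045 × 23.95/√30 = 8.94; 2.045 × 29.69/√30 = 11.09). That is what one sees when the baseline carries no sampling error in the interval. The table's model is not described, so it illustrates the mechanism and does not measure it for VAS.

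**The case against.** The strongest reply is that a baseline-covariate repeated-measures model with LS means is conventional, and that its interval is valid conditional on the observed baseline mean (simulated conditional coverage is about 95%). That is true. On this view the defect is an unstated inferential target, not a faulty calculation. But neither document states that target, and a reader of a single-arm mean change will take the interval to refer to the population sampled.

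The second reply is about size, and most of it stands. The only data in the documents show follow-up more variable than baseline: NOSE follow-up SDs at 1 to 12 months are 23.95 to 29.69, while a baseline confined to 55–100 has an SD of at most about 22.5. That favours the lower rows of the coverage table. NOSE is an imperfect guide, though, because eligibility truncates baseline NOSE and sets no limit on baseline VAS.

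Third, no decision rests on these intervals. Protocol 10.2 has no other formal hypotheses, and Protocol 10.4.9 calls the other endpoints supportive. If the N, mean and SD summaries in Protocol 10.4.1 are applied to VAS change, a reader could form the paired interval. This limits the consequence but leaves the planned interval as it is.

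Three stronger readings are tempting and not supported:

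- The prior study's 1-week row (6.14 against 8.50, ratio 0.72) might suggest coverage near 84% and widening of about 40%. This study collects no VAS at 1 week.
- One might infer that the intervals are not comparable from 1 to 24 months. The matching-visit ratios span only 0.94 to 0.97. The 18-month row has 15 subjects and probably borrows from earlier visits, and there is no 24-month row.
- One might call VAS the only continuous measure of benefit. Protocol 10.4.8 and 10.4.11 also evaluate change in NOSE score, although no whole-cohort model for it is spelled out.

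**Conclusion.** The point holds for the mean change in the population sampled: as specified, the VAS intervals omit the sampling variation of the baseline mean and are too narrow unless the slope of follow-up on baseline is 1. The omission follows from the model; its size rests on assumptions. If VAS behaves as NOSE did at the matching prior-study visits, the shortfall is about 1 to 2 points. With equal SDs and correlations of 0.1 to 0.7 it is about 2 to 9 points. With SDs of 15 and 25 it is about 0 to 3 points, and it reaches about 4 at k = 1.5 and rho 0.1. The LS mean itself is not biased by this, and the exact test of the 6-month responder proportion is untouched. This is a correctable fault in the error bars of a secondary, descriptive endpoint, and it does not threaten the study's main conclusion.

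**What to change.** In SAP 4.4.2, make the pre-decongestant baseline VAS the first response in the repeated-measures vector. Use visit as a categorical factor with baseline as one level and an unstructured covariance, and report each visit-minus-baseline contrast with its 95% interval. Drop baseline VAS and its visit interaction as covariates from the reported model, or keep that model as supportive and say that its intervals are conditional on the observed baseline mean.

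With complete data this reproduces the paired mean change and its paired standard error. It keeps likelihood-based handling of missing visits and removes the data-dependent interaction choice. It needs a short SAP edit, a small programming change and no new data.

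The costs are modest. Intervals widen by about 3% to 7% at the prior-study ratios (1/0.973 to 1/0.936), and by more if the SDs are similar and the correlation is low; in the worked case they widen by 15% (3.22/2.79). The covariance matrix grows from 6 × 6 to 7 × 7 (21 to 28 parameters). The compound-symmetry fallback would then force one variance on baseline and follow-up alike, so its wording should be revisited in the same edit.

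### If the VAS repeated-measures model fails to converge, SAP 4.4.2 drops straight to compound symmetry; a fallback with a separate variance per visit would be safer

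*SAP*

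**What the plan says.** SAP 4.4.1 lists as a secondary endpoint: "Change in nasal airway obstruction from baseline to 1,3, 6, 12, 18 and 24 months as reported by subjects on the VAS scale". SAP 4.4.2 gives the model: a mixed model for repeated measures on observed data, with visit, baseline VAS and a baseline-by-visit term that is kept if significant. On the covariance it says "An unstructured covariance matrix will be used to model the within-subject errors", followed by "If this model does not converge, a compound symmetry covariance matrix will be used". The output is stated as "Least-square mean change from baseline and corresponding 95% confidence intervals will be reported". No other structure is named, and neither is an empirical standard error, so the default reading is model-based standard errors.

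The paragraph opens by calling the modelled variable the primary endpoint. Its covariate is baseline VAS, however, and Protocol 10.4.3 assigns this model to the secondary VAS change. The primary responder endpoint has its own exact test in SAP 4.2.2.

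**The concern.** An unstructured matrix for six visits has 6 × 7 / 2 = 21 parameters. Compound symmetry has two: one variance and one correlation. The fallback therefore moves from the most flexible structure to nearly the most rigid, with nothing in between.

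If spread differs by visit, a common variance is too large where spread is small and too small where it is large. Intervals are then too wide at the first group of visits and too narrow at the second. Here the visits at risk of being too narrow are 18 and 24 months. Protocol 6.2 puts absorption of the implant at about 18 months, so readers will look at those visits for durability. A fallback is used only when the planned fit has failed, so it should be sound in that situation.

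**Working it through.** **Plan's own figure.** None exists for this model: the documents give no SD, precision target or power for VAS. The prior study's NOSE-change SDs are used as a stand-in.

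**Inputs (Protocol 2.2 table, SD of change from baseline).** 25.56 (1 month, n = 30), 27.84 (3 months, n = 29), 31.28 (6 months, n = 30), 31.23 (12 months, n = 29), 36.24 (18 months, n = 15). The 24-month SD is assumed equal to the 18-month SD, then varied.

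**Step 1: pooled SD under compound symmetry.** With balanced data the model uses the average variance at every visit:

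SD_pool = √[(25.56² + 27.84² + 31.28² + 31.23² + 36.24² + 36.24²) / 6] = √(6008.8 / 6) = 31.65.

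(With the five observed visits only: √(4695.5 / 5) = 30.64.)

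**Step 2: width and coverage.** Width relative to the correct width at visit k is SD_pool / SD_k. Coverage is 2Φ(1.96 × SD_pool / SD_k) − 1.

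| Month | SD | Relative width | Coverage |
|---|---|---|---|
| 1 | 25.56 | 1.24 | 98.5% |
| 3 | 27.84 | 1.14 | 97.4% |
| 6 | 31.28 | 1.01 | 95.3% |
| 12 | 31.23 | 1.01 | 95.3% |
| 18 | 36.24 | 0.87 | 91.3% |
| 24 | 36.24 (assumed) | 0.87 | 91.3% |

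**Step 3: other assumptions about the spread.**
- 24-month SD of 40: pooled SD 32.39; coverage 92.0% at 18 months and 88.8% at 24 months.
- SDs of the NOSE score instead of its change (23.95, 26.90, 29.69, 29.17, 33.32, last repeated): pooled SD 29.58; coverage 98.5% at 1 month and 91.8% at 18 and 24 months.
- Spread flat after 6 months (31.23 at 12, 18 and 24 months): pooled SD 29.81; coverage 97.8% at 1 month and 93.8-93.9% from 6 months on.
- Constant spread: 95% throughout.

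**Step 4: simulation with dropout.** Assumptions: 170 subjects, six visits, the SDs in the table, correlation 0.7 between adjacent visits and decaying, missing-at-random monotone dropout of about 10% by 24 months, 600 runs, no interaction term. Monte Carlo standard error is √(0.95 × 0.05 / 600) = 0.9 points at 95%.

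| Month | 1 | 3 | 6 | 12 | 18 | 24 |
|---|---|---|---|---|---|---|
| Compound symmetry, coverage % | 99.0 | 98.2 | 95.7 | 94.7 | 89.5 | 91.2 |
| Unstructured, coverage % | 94.0 | 95.3 | 94.8 | 95.0 | 93.3 | 95.5 |
| Compound symmetry, mean width | 9.50 | 9.58 | 9.65 | 9.72 | 9.78 | 9.85 |
| Unstructured, mean width | 7.76 | 8.46 | 9.60 | 9.67 | 11.34 | 11.42 |

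The unstructured fit stands for any structure with visit-specific variances. The heterogeneous structures and sandwich errors were not simulated separately, and the convergence of production software was not tested.

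**Step 5: size in millimetres.** With 150 subjects and no baseline adjustment, the 18-month half-width would be 1.96 × 31.65 / √150 = 5.1 mm instead of 1.96 × 36.24 / √150 = 5.8 mm, about 0.7 mm on a 100 mm scale.

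**Step 6: how firm is the growth?** The 95% interval for an SD is s√[(n − 1)/χ²]. It is 20.4 to 34.4 at 1 month and 26.5 to 57.2 at 18 months. These overlap.

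**The case against.** The case for leaving the text alone is substantial.

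- **The fallback may never be used.** The unstructured fit is the planned analysis, and 21 covariance parameters are modest for 150 to 170 subjects. Protocol 5.3 targets 150 subjects completing 24 months and allows telephone or mailed forms at 18 and 24 months. This stands. On the other side, Protocol 5.1 asks subjects to agree to follow-up only through twelve months, the schedule in Protocol 7.7 requires re-consent for the later visits, and in the prior study "15 out of 30 subjects completed 18 months of follow up". Sparse late data make an unstructured fit harder, but the documents give no basis for a probability of failure.
- **The evidence on spread is indirect.** It is NOSE rather than VAS. It comes from 30 subjects without septal or turbinate treatment (Protocol 2.3.3). The SD is flat between 6 and 12 months, and the 18-month value rests on 15 subjects. A reader might infer that the prior data contradict equal variances. They do not go that far; they suggest that spread may grow.
- **Little hangs on it.** Protocol 10.2 sets no formal hypothesis beyond the primary, and SAP 4.1.1 makes other p-values descriptive. A reader might infer from the opening words of SAP 4.4.2 that the primary result is exposed. It is not, because it is tested by an exact binomial method.
- **The interaction term.** A reader might also infer that keeping the baseline-by-visit term only if significant distorts the intervals, or that the rule has no threshold. Neither is supported. SAP 4.1.1 supplies a default 2-sided 5% level. In the simulation, keeping or dropping the term moved unstructured coverage by at most about 0.7 points and width by at most about 1.3%, even with baseline slopes running from −1.0 to −0.5 across visits.

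**Conclusion.** The point holds in conditional form and is minor. If the unstructured fit fails, and if VAS spread grows over time as NOSE spread appeared to, the stated fallback gives intervals that are too wide at 1 month (coverage about 98-99%) and too narrow at 18 and 24 months (about 89-91%), with 6 months close to nominal. With spread flat after 6 months, the late shortfall is only about one point, and with constant spread there is none.

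The result rests on three assumptions: that the fallback is triggered, that NOSE-change SDs are a fair guide to VAS, and that the unobserved 24-month SD is at or near the 18-month value. It does not show that the VAS intervals will be wrong under the planned analysis. The case for changing the text is that the replacement is better in the one situation where it applies and costs almost nothing.

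**What to change.** In SAP 4.4.2, replace the compound symmetry sentence with an ordered list of structures that allow a separate variance per visit, for example heterogeneous Toeplitz and then heterogeneous compound symmetry. State that empirical (sandwich) standard errors will be used for any structure other than unstructured. Keep both parts: the sandwich estimator repairs the standard errors, but under missing-at-random dropout the point estimates still depend on a reasonable covariance model. In the same edit, name the modelled variable as the VAS change instead of the primary endpoint.

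The cost is one or two SAP sentences and slightly more programming. If the fallback is used and spread does grow, late intervals will be wider. In the simulation the 18-month width was 11.34 with visit-specific variances against 9.78 under compound symmetry (11.34 / 9.78 = 1.16), while the 1-month width fell from 9.50 to 7.76. The primary analysis and the sample size are unaffected.
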